Univariate and multiple logistic regression (MLR) methods will be used to investigate the impact of various explanatory covariates (e.g. demographic and disease characteristics, co-morbidities, type of treating institution, and prior treatment for CHC and response outcome in treatment experienced patients) on SVR12. These analyses will be of exploratory nature, data driven, and will be performed for various CP analysis groups since not each covariate might be predictive in each patient group. Furthermore, the fact that treatment regimens will differ in the various patient groups has to be taken into account, when selecting the patient groups for each MLR analysis. Backward selection procedures will be applied to generate the final MLR models which will consider only covariates in the selection procedure with a p-value  $<0.25$  in the corresponding univariate logistic regression analysis. A p-value  $<0.05$  will be used for the covariates to stay in the model in a backward elimination step. Logistic regression methods will also be used to investigate the impact of treatment adherence on SVR12.

All safety variables will be summarized for patients in the SP using descriptive statistical methods stratified by the type of combination treatment and scheduled treatment duration.

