**Table 1 - SVR12 rates in clinical trials:**

Population and treatment duration	Genotype	SVR12 ABBVIE REGIMEN + RBV	SVR12 ABBVIE REGIMEN alone
Non-cirrhotic, treatment-naïve (12 weeks)	1a	95-97% (SAPPHIRE-I, PEARL-IV)	90% (PEARL-IV)
	1b	98-99.5% (SAPPHIRE-I, PEARL-III)	99% (PEARL-III)
Non-cirrhotic, treatment-experienced (12 weeks)	1a	96% (SAPPHIRE-II)	n.a.
	1b	97% (SAPPHIRE-II, PEARL-II)	100% (PEARL-II)

These results suggest that the ABBVIE REGIMEN with RBV is the optimal regimen for genotype 1a infected patients, while patients with genotype 1b do not require RBV.

The TURQUOISE-II [60] study explored the efficacy of the ABBVIE REGIMEN in the traditionally most difficult-to-treat cirrhotic patients. This large study enrolled exclusively genotype 1 infected patients with cirrhosis, including treatment-naïve and treatment-experienced individuals. All patients received the ABBVIE REGIMEN with RBV and were

---

Confidential Information

No use or disclose outside AbbVie is permitted without prior written authorization from AbbVie

---

randomized to 12 or 24 weeks of therapy. Overall 92% and 96% of patients achieved SVR following treatment for 12 or 24 weeks, respectively. Analysis of subgroups demonstrated that the small difference in SVR between treatment arms was due largely to the subgroup of genotype 1a treatment-experienced prior null responders treated for 12 weeks who achieved an SVR of 80%. This subgroup of patients achieved an SVR of 93% when treated for 24 weeks. Among genotype 1a infected patients, partial responders and relapsers had higher SVR rates than null responders in the 12 week treatment group, while similar SVR rates were seen among the null responders, partial responders and relapsers treated for 24 weeks, suggesting that the longer duration of 24 weeks is required only for cirrhotic genotype 1a null responders. SVR rates were very high across all subgroups in genotype 1b treatment-experienced patients treated for 12 and 24 weeks.

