#### 9.7.3.3 Statistical Methods for Analysis of Effectiveness Variables

The simple percentage of patients achieving SVR12 will be calculated and an exact two-sided 95% confidence interval (CI) of the percentage will be computed based on the Clopper-Pearson method.

Corresponding methods will be used for other response rates (EoT response rate, relapse rate, viral breakthrough). The relapse rates will be estimated in patients of the CP analysis groups with EoT response and sufficient HCV RNA measurements post-treatment. Viral breakthrough rates will be estimated in all patients of the CP analysis groups, who have at least one undetectable HCV RNA measurement on-treatment and at least one on-treatment or EoT measurement thereafter.

Univariate and multiple logistic regression (MLR) methods will be used to investigate the impact of the following explanatory covariates on SVR12:

- Key demographic information
- Mode of CHC infection
- HCV RNA level at baseline
- Most recent stage of liver fibrosis
- HCV genotype and subtype (if available)
- Type of treating institute
- Liver and/or CHC related co-morbidities
- Key clinical chemistry and hematology laboratory variables at baseline
- In treatment experienced patients only:
  - Most recent prior treatment for CHC
  - Outcome of most recent prior CHC treatment

Further details and additional covariates will be specified in the SAP.

These analyses will be of exploratory nature, data driven, and will be repeatedly performed for various CP Analysis Groups, since not each covariate might be predictive in each patient group. Furthermore, the fact that treatment regimens will differ in the various patient groups has to be taken into account, when selecting the patient groups for each MLR analysis. Backward selection procedures will be applied to generate the final MLR models which consider only covariates in the selection procedure with a p-value

---

Confidential Information

No use or disclose outside AbbVie is permitted without prior written authorization from AbbVie

<0.25 in the corresponding univariate logistic regression analysis. A p-value <0.05 will be used for the covariates to stay in the model in a backward elimination step. Logistic regression methods will also be used to investigate the impact of treatment adherence on SVR12.

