4.2.6.3 CHC treatment history

For treatment-experienced patients the most recent prior treatment and the outcome to prior treatment as reported by the investigator in the eCRF (Null response, Partial response, Breakthrough, Relapse, Sustained virological response (SVR) followed by reinfection, Discontinued [and none of the above], Unknown/ None of the above) will be summarized in frequency tables. In addition to the frequency of each medication (IFN alpha, PEG IFN-alpha, IFN NOS, PEG IFN NOS, Ribavirin, DAA), the frequency of the combinations (pegIFN alpha + RBV, pegIFN alpha + RBV + Telaprevir, XXX) will be summarized.

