- Other co-morbidities (every patient not reporting the respective co-morbidity is considered as not having the respective co-morbidity)
 - Depression (No [reference], Yes)

- Diabetes mellitus (No [reference], Type 1/Type 2)
 - Hypertension (No [reference], Yes)
 - Immunologically mediated disease (No [reference], Yes)
 - Hypothyroidism (No [reference], Yes)
 - Alcohol use (None [reference], Yes –occasional, Yes –regular, Exdrinker)
 - Key clinical chemistry and hematology laboratory variables at baseline
 - ALT ratio (continuous, see 4.2.6.5)
 - AST ratio (continuous, see 4.2.6.5)
 - Platelets [$10^9/L$] (continuous)
 - Prior treatment status (HCV treatment naïve [reference], HCV treatment experienced)

Additionally, an interaction term for cirrhosis status and genotype will be considered. If the most recent stage of liver fibrosis status (No cirrhosis/Transition to cirrhosis vs Cirrhosis), the genotype (G4, G1b vs G1a) or the interaction of both remains in the final model, then additional MLR might be considered for the subgroups concerned, taking into account the treatment regimen (e.g. in cirrhotic G1 patients: RBV vs no RBV and 12 wks vs 24 weeks).

The categories pre-specified above could be modified in the analyses if this is supported by the data (e.g. categories could be combined, if their impact on SVR12 is similar). Furthermore, continuous variables can be replaced by categorical variables.

Adherence

Adherence will be displayed for the CP by genotype and cirrhosis status and for the SP by treatment regimen and cirrhosis status. Summary statistics (n, mean, median, standard deviation [SD], and range) will be generated for continuous variable. Numbers and percentages of patients will be presented for categorical variables.

- Adherence to Abbvie regimen (% of target dose [adherence=cumulated number of pills taken /(initial prescribed number of pills x planned duration)])
 - >105%
 - >95%--<=105%
 - >80%--<=95%
 - >50%--<=80%
 - <=50%
- Adherence to ribavirin (% of target dose [adherence=cumulated dose taken /(initial prescribed dose x planned duration)])

- >105%
 - >95%-<=105%
 - >80%-<=95%
 - >50%-<=80%
 - <=50%
- Percentage of actual treatment duration in relation to the target duration of ABBVIE regimen taken
- Deviating duration of ABBVIE regimen
 - Early discontinuation (actual duration is shortened for more than 7 days)
 - Not deviated
 - Exceedance (actual duration is prolonged for more than 7 days)

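### The SAP drops two protocol covariates on prior HCV treatment without saying so, so no prespecified SVR12 model tests prior null response

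*SAP*

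**What the plan says.** **Protocol.** Section 9.7.3.3 lists the covariates for the univariate and multiple logistic regressions on SVR12. For treatment-experienced patients only, it names "Most recent prior treatment for CHC" and "Outcome of most recent prior CHC treatment". The Data Analysis part of the abstract names the same pair: "prior treatment for CHC and response outcome in treatment experienced patients". On what the SAP may change, 9.7.3.3 says "Further details and additional covariates will be specified in the SAP". It does not mention taking covariates out.

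**SAP.** The list under SVR12 (Exploratory Analyses) in 4.2.7.2.1 has one variable for prior therapy: "Prior treatment status (HCV treatment naïve [reference], HCV treatment experienced". The models are to be run in the CP, and none is restricted to experienced patients. The CP analysis groups in SAP 4.2.1 use fibrosis status and genotype only, although Protocol 9.7.2 also based them on treatment experience. Section 4.2.6.3 summarises "the outcome to prior treatment as reported by the investigator in the eCRF", with null response as one of its categories, in frequency tables. Table 8 of the SAP lists no SVR12 output by prior response.

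**Evidence in the protocol.** Section 7.1, after Table 1, attributes the small difference between the two durations in the cirrhosis study largely to "genotype 1a treatment-experienced prior null responders treated for 12 weeks who achieved an SVR of 80" percent. It adds: "This subgroup of patients achieved an SVR of 93% when treated for 24 weeks".

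**The concern.** Secondary objective 2 is to find predictors of virological response. Prior-treatment outcome is a predictor that the protocol committed to examine, and its own background gives a reason to do so. A naive-versus-experienced variable puts null responders in one group with relapsers and partial responders. If null responders do worse, the other experienced patients dilute the difference. A weak coefficient for treatment experience would then say little about null response.

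There is also a reporting problem. The SAP announces other departures from the protocol: the upper limit of the SVR12 window (4.1.1), the replacement of shift tables (4.2.8.4) and the interim timing (4.2.9). It is silent here, so a reader cannot tell a decision from an oversight.

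**Working it through.** **1. The plan's own figure.** The base sample size is not in dispute. Clopper-Pearson limits for 417 patients at 90% are 86.71 to 92.71, width 6.00, as stated. Allowing 5% non-evaluable gives 417 / 0.95 = 439, against 440 planned.

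**2. The two lists compared.**

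| Item | Protocol 9.7.3.3 | SAP 4.2.7.2.1 |
|---|---|---|
| Most recent prior treatment | listed, experienced patients | absent |
| Outcome of that treatment | listed, experienced patients | absent |
| Naive or experienced | not in this list | listed, whole CP |
| Model in experienced patients | implied | none |
| Removal declared | not applicable | no |

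This comparison carries the point. The arithmetic below only illustrates what pooling does.

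**3. Inputs for the illustration.** The documents give neither the share of experienced patients nor the share of null responders among them. Both are assumptions. Power is the two-sided 5% normal approximation for two proportions:

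power = Φ[(|p1 − p2| − 1.96·SE0) / SE1],

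where SE0 uses the pooled proportion and SE1 the separate ones. It counts only the expected direction, so values can fall below 5%. It is crude for small groups.

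**4. Broad case: every null responder has SVR 80%.** Assume N = 417, 30–50% experienced, 10–40% of these null responders, and 96% SVR in everyone else.

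- Diluted rate in experienced patients: with 10% null responders, 0.1 × 80 + 0.9 × 96 = 94.4%; with 40%, 0.4 × 80 + 0.6 × 96 = 89.6%.
- Example, 30% experienced and 10% null: 12 null responders against 113 other experienced. Pooled rate (12 × 0.80 + 113 × 0.96) / 125 = 0.9446; SE0 = 0.0694; SE1 = 0.1169. Power = Φ[(0.16 − 0.1361) / 0.1169] = Φ(0.20) = 58%. Naive versus experienced in the same setting: 12%.
- Over all these settings: null versus other experienced 58–94%; naive versus experienced 12–72%.
- If null responders reach 93% instead: 12–17% against 4–9%.

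**5. Narrow case: the 80% applies only where the protocol reports it.** Take N = 440 × 0.95 = 418, 40% experienced (167), and 42 or 67 null responders (25% or 40% of 167). Assume 10–30% of the null responders are cirrhotic genotype 1a treated for 12 weeks and fail at 20%, and everyone else fails at 4–7%.

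- Lowest case, 42 null responders: failure 0.1 × 20 + 0.9 × 7 = 8.3%. Odds ratio (0.083 / 0.917) / (0.07 / 0.93) = 1.20; power against all others about 6%.
- Highest case, 67 null responders: failure 0.3 × 20 + 0.7 × 4 = 8.8%. Odds ratio (0.088 / 0.912) / (0.04 / 0.96) = 2.32; power about 42%.
- Naive versus experienced over the same settings: about 3–15%, lower in each one.

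**6. Events available.** At 5–10% failure, 417 patients give 21–42 failures. The SAP list already holds 27 candidate variables by my count, plus an interaction term.

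**7. The availability rule.** SAP 4.2.7.2.1 leaves out a variable with data in fewer than 80% of the patients analysed. Prior outcome exists only in experienced patients. As a separate covariate in the whole CP it would fail the rule unless at least 80% of the CP were experienced.

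**The case against.** The strongest objection is that the protocol does not show a general null-responder effect. Section 7.1 gives the 80% for cirrhotic genotype 1a null responders treated for 12 weeks. At 24 weeks the prior-response groups were similar, and experienced genotype 1b patients had very high rates throughout. Table 1 of the protocol shows 96–100% in non-cirrhotic experienced patients. This is an effect tied to genotype, cirrhosis and duration, and a main effect for null response would capture only part of it. That stands, and it is why the narrow case above is needed.

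Nor is it the only response difference the protocol reports. Genotype 1a without versus with ribavirin (90% against 95–97%) and genotype 4 (91% against 100%) are others.

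Second, the SAP leaves room. The analyses are exploratory and data driven, categories may be modified if the data support it, and further subgroup models might be considered. That is also true, but these clauses commit to nothing, and the example given for categories is combining them, not splitting them. They do not cover two omitted covariates.

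Third, with 21–42 failures any null-responder estimate will be fragile. This limits what the analysis can show. It does not explain why these two protocol covariates went while many others with no stated prior evidence were added.

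**Conclusion.** The point holds as an undeclared omission of two protocol covariates, with the result that no prespecified model tests prior null response. It does not affect the primary SVR12 estimate. It is a worthwhile, inexpensive correction to an exploratory secondary analysis.

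The size of the loss is unknown. Power for null responders against their comparison group ranges from about 6% (20% failure confined to cirrhotic genotype 1a at 12 weeks) to about 94% (80% SVR in all null responders). What does not change is the ordering: in every matched setting examined, separating null responders gave more power than naive versus experienced. All of this rests on assumed subgroup shares.

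A reader might infer more, and the documents do not support it:

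- That null response cannot be tested. The data are on the eCRF and the SAP permits changes to categories; the test is simply not prespecified.
- That null response is the one known predictor, or that a null finding would be uninterpretable. The reported effect is conditional, and other differences are reported.
- That a well-powered test (75–86%, falling to 23–44% for naive versus experienced) has been given up. That needs 20% failure in every null responder and 7% in everyone else, which Section 7.1 does not show.

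**What to change.** - Restore both protocol covariates in a logistic model restricted to treatment-experienced CP patients.
- In the whole-CP model, replace the two-level variable with naive (reference), prior null response, and other experienced with known outcome. Keep unknown outcome as a separate level or handle it in a sensitivity analysis, so that unrecognised null responders are not counted as non-null. With naive as a level, the variable is defined for nearly everyone and is not removed by the 80% rule.
- Tabulate SVR12 with its confidence interval by prior-response category in the CP, and by genotype and cirrhosis status where numbers allow. The table can show the conditional pattern that a main effect would miss.
- If the covariates are not restored, declare and justify their removal as a departure from the protocol, as the SAP does elsewhere.

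The cost is SAP wording, one or two parameters in the whole-CP model, the restricted model and one table, all from data already collected. The downside is sparse categories. With 21–42 failures in the whole CP, and about 6–21 in experienced patients if 30–50% are experienced and fail at the same 5–10% (125 × 0.05 to 208 × 0.10), the restricted model must be kept small, and all results remain exploratory.

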4.2 Statistical and Analytical Methods

4.2.1 Analysis Populations and Analysis Groups

Population of Patients Enrolled [EP]

The population of patients enrolled comprises all patients who voluntarily sign and date an informed consent prior to inclusion into the study and data were captured in the eCRF.

Target Population [TP]

Patients will be included if the following applies:

- Age at least 18 years
- Confirmed CHC with genotype 1 and/or 4 only, receiving combination therapy with the interferon-free ABBVIE REGIMEN \pm RBV. The prescribed ABBVIE REGIMEN needs to be known.
- Have voluntarily signed and dated an informed consent prior to inclusion into the study
- Must not be participating or intending to participate in a concurrent interventional therapeutic trial

Core Population [CP]

The core population is defined as all patients of the target population (TP) (definition see above), who are adequately treated according to the standard of care and within local label recommendations for their specific disease characteristics (cirrhotic status, genotype). The following patients will be excluded from the CP:

- Patients with unknown fibrosis status
- Cirrhotic patients with genotype 1a not receiving ribavirin
- Patients with genotype 1 for whom 2DAA instead of 3DAA is prescribed
- Patients with genotype 4 not receiving RBV

Non-Core Population [NCP]

Patients in the TP who are not in the CP.

Core Population with Sufficient Follow-up [CPSFU {12, 24}]

In addition, the core population with sufficient follow-up data regarding SVR12 or SVR24, respectively, is defined as all CP patients,

- who have evaluable HCV RNA data ≥ 70 days or >126 days, respectively, after the last actual dose of the ABBVIE REGIMEN
- or a HCV RNA value ≥ 50 IU/mL at the last measurement
- or had HCV RNA <50 IU/mL at the last measurement, but no HCV RNA measurement ≥ 70 days or >126 days, respectively, after the last actual dose of the ABBVIE REGIMEN due to reasons related to safety (e.g. dropped out due to adverse event) or virologic failure (e.g. virologic failure such as relapse is reported in the electronic case report form (eCRF) but date and value of the corresponding HCV RNA test is missing).

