Virological response rates and non-response categories will be displayed for patients who completed treatment with AbbVie regimen, as well.

SVR12 (Exploratory Analyses)

Univariate and multiple logistic regression (MLR) methods will be used to investigate the impact of various explanatory covariates (patient and disease characteristics) at baseline on SVR12.

These analyses will be of exploratory nature, data driven, and will be performed for CP population. Univariate logistic regression will be performed first and then backward selection procedures will be applied to generate the final MLR model. A p-value <0.05 will be used for the covariates to stay in the model in a backward elimination step. If the percentage of patients with available data for a variable is lower than 80% of the patient group analyzed, then this variable will not be considered in the MLR analysis.

The variables to be considered are as follows:

- Key demographic information
 - Age (continuous)
 - Gender (Female [reference], Male)
 - Race/ethnic origin (White/Caucasian [reference], Black, Asian/Oriental, Other [all other races]); at least two categories with at least 10% of the patients each have to exists, so that this variable will be considered
 - Weight (continuous)
 - BMI (continuous)
 - IL28B, rs12979860 (CC [reference], CT or TT); patients with unknown genotype are excluded from the respective analyses.
- CHC disease characteristics
 - Years since diagnosis (continuous)
 - Mode of CHC infection (Drug use [reference], Other [all other answers excluding unknown], unknown);
 - Most recent stage of liver fibrosis (No cirrhosis/Transition to cirrhosis [reference], Cirrhosis; for definition see 4.2.6.2);
- HCV RNA level at baseline (\log_{10} IU/mL)
- HCV genotype(G1a*, G1b, G4; for definition see section 4.2.6.2)
- Type of treating institute (Private Practice / Private Hospital, Academic / University Hospital, General Hospital, Other)
- Co-infections (every patient not reporting the respective co-infection is considered as not having the respective co-infection)
 - HIV(No [reference], Yes)
 - HBV(No [reference], Yes)
- Liver and/or CHC related co-morbidities (every patient not reporting the respective co-morbidity is considered as not having the respective co-morbidity)
 - Liver transplantation (No [reference], Yes)
 - Steatosis (non-alcoholic) (No [reference], Yes)
 - Decompensated liver disease (No [reference], Yes)

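### The SVR12 predictor model pools all core-population regimens without a ribavirin or duration term, and any look at regimen is optional and waits on a significance test

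*SAP*

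**What the plan says.** **SAP 4.2.7.2.1, SVR12 (Exploratory Analyses).** The regressions examine "various explanatory covariates (patient and disease characteristics) at baseline on SVR12". On the analysis set: "These analyses will be of exploratory nature, data driven, and will be performed for CP population". The list runs to 27 candidates by my count, plus a cirrhosis-by-genotype interaction. RBV use, two versus three antivirals and planned duration are not on it. On selection: "A p-value <0.05 will be used for the covariates to stay in the model in a backward elimination step".

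Regimen appears only at the end. The trigger is that fibrosis stage, genotype "or the interaction of both remains in the final model". What follows the trigger is optional: "then additional MLR might be considered for the subgroups concerned, taking into account the treatment regimen". The example given is "in cirrhotic G1 patients: RBV vs no RBV and 12 wks vs 24 weeks".

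**Protocol 9.7.3.3.** The regressions are to be repeated for various CP analysis groups, and "the fact that treatment regimens will differ in the various patient groups has to be taken into account, when selecting the patient groups". The protocol's own covariate list has no regimen term either.

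**SAP 4.2.1, Core Population.** Three regimen exclusions apply: "Cirrhotic patients with genotype 1a not receiving ribavirin", genotype 1 patients prescribed two antivirals rather than three, and genotype 4 patients without RBV. Planned duration is not mentioned.

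**SAP Tables 6 and 8.** SVR12 is tabulated by genotype and cirrhosis. Regimen is tabulated by the same groups. No listed table gives SVR12 by regimen.

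**The concern.** Regimen is assigned largely from the factors under study. If more intensive treatment works, it narrows the difference in SVR12 between harder- and easier-to-treat patients. A model without regimen then estimates the factor together with the treatment it attracted. The plan looks at regimen only when that narrowed difference is still significant, and even then the look is optional.

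Predictive factors of response are secondary objective 2. A finding that cirrhosis or genotype does not predict SVR12 could mean that the factor has no bearing on response, or that treatment choice compensated for it. The listed outputs would not let a reader tell these apart. The SAP flags some of its departures from the protocol (the SVR12 window, the laboratory shift tables, the interim analysis), but not the move from repeated group-wise regressions to one pooled model.

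**Working it through.** **1. The plan's own sizing figure.** Clopper-Pearson limits for n = 417 and 90%, with the count left unrounded at 375.3, are 86.71% to 92.71%, width 6.00%, as in SAP Table 1. Allowing 5% non-evaluable: 417/0.95 = 438.9, so 439 against the stated 440. No sizing is given for the predictor model. Expected non-responders: 417 × 0.10 = 41.7, or 417 × 0.05 = 20.9, so about 21 to 42 for 27 candidates.

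**2. Where regimen can vary inside the CP.**

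| Cell | RBV under the CP rules |
|---|---|
| G1a, cirrhotic | always |
| G1a, non-cirrhotic | free |
| G1b, either | free |
| G4, either | always |

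Duration is free everywhere. Dasabuvir is fixed for genotype 1. So regimen is not fully determined by genotype and cirrhosis, and the SAP's own example presupposes variation in cirrhotic G1.

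**3. How far treatment can narrow a contrast, using rates in Protocol 7.1.** Odds are p/(1−p).
- RBV within naive non-cirrhotic G1a, 95–97% with and 90% without: 19/9 = 2.1 to 32.3/9 = 3.6.
- G1b against G1a, neither on RBV (99% and 90%): 99/9 = 11.0.
- G1b without RBV against G1a with RBV at 95, 96 and 97%: 99/19 = 5.2, 99/24 = 4.1, 99/32.3 = 3.1.
- Non-cirrhotic at an assumed 97% against cirrhotic at 92% (12 weeks): 32.3/11.5 = 2.8. Against 96% (24 weeks): 32.3/24 = 1.35.

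Power for one such contrast at two-sided 0.05 is Φ((|p1 − p2| − 1.96·SE0)/SE1), with SE0 pooled and SE1 unpooled. Example: 100 G1a at 95% and 317 G1b at 99% give SE0 = 0.0159 and SE1 = 0.0225, so Φ((0.040 − 0.0312)/0.0225) = Φ(0.39) = 0.65. With 100 to 267 G1a patients among 417 (assumed):
- neither group on RBV: 0.95–0.98
- G1a treated with RBV, G1b without: 0.23–0.69
- cirrhosis (83 to 167 patients, assumed), treated 12 weeks: 0.54–0.62
- cirrhosis, treated 24 weeks: about 0.08

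These compare differently treated cells across trials. They show that as-treated contrasts shrink. They do not measure the bias from omitting RBV in the pooled model.

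**4. Bias in a model closer to the SAP's.** These are simulations with genotype and cirrhosis in the model, RBV fixed where the CP rules fix it, n = 417 and a true cirrhosis odds ratio of 0.40. The regimen mix is assumed.
- RBV helps only G1a and G4: cirrhosis odds ratio without an RBV term 0.43–0.52.
- RBV also helps G1b: 0.53–0.62.

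A second set used about 26 non-responders, a G1a/G1b/G4 mix of 25/60/15%, 35% cirrhotic, and RBV in 70–90% of non-cirrhotic G1a, 50–90% of cirrhotic G1b and 10% of other G1b. It gave 0.41–0.45 with an RBV odds ratio of 3 in G1a and G4 and 1 in G1b, and 0.50–0.64 with an odds ratio of 2 in G1b as well. Adding RBV to the model removed the cirrhosis bias.

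**5. What the added term does to the trigger.** Without RBV, the chance that the trigger opens was 52–86% in the first set. Keeping RBV in lowered it from 86% to 78% when RBV had no effect, and from 68% to 56% when RBV tracked genotype closely. In a separate genotype-only simulation, power for genotype went from 0.82–0.89 to 0.85–0.94 with RBV in 50% of G1a and 10% of G1b, but from 0.36–0.59 to 0.32–0.36 at 95% and 5%. These probabilities depend heavily on the assumed genotype effect, so the conclusion does not rest on them.

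**The case against.** **Describing factors as treated is legitimate.** The objective concerns routine practice. If label-treated cirrhotic patients respond as well as others, cirrhosis does not predict response in that setting. SVR12 by genotype and cirrhosis is reported whatever the selection does. This stands, and it is why the planned model should be kept. It does not justify leaving the regimen-adjusted view to an optional step behind a significance test.

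**A reader might infer that the protocol demands a regimen covariate in every regression.** It does not. Its requirement concerns the choice of patient groups. The departure is dropping the repeated group-wise analyses and making regimen optional.

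**A reader might infer that regimen will hide cirrhosis and keep the trigger shut when it matters most.** A simulation with cirrhosis alone in the model, about 26 non-responders and a uniform RBV odds ratio of 2 or 3 gives a cirrhosis odds ratio of 0.59 or 0.74 against a true 0.40, with cirrhosis significant in 27% or 11% of runs. That is not the SAP's model, which includes genotype, and the trigger also opens on genotype or the interaction. Nor do the documents support a uniform RBV effect: Protocol Table 1 shows no gain in non-cirrhotic G1b (98–99.5% with and 99% without in naive patients; 97% and 100% in experienced patients). They give no RBV comparison in cirrhotic G1b, so an effect there is neither shown nor excluded.

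**Forcing regimen in has a price.** In cirrhotic G1a and in G4, adjustment is extrapolation, because every CP patient there receives RBV. Protocol 9.7.7 expects about 95% of the interim set on 12 weeks. If that held overall, about 0.05 × 417 = 21 patients would have 24 weeks, too few for a stable duration term. This stands and limits the fix.

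**Conclusion.** The concern holds as a weakness in an exploratory analysis that serves secondary objective 2. The SAP pools CP regimens, carries no RBV or duration term, and makes any look at regimen optional and dependent on significance, which is weaker than Protocol 9.7.3.3. The planned coefficients mix each factor with the treatment it attracted and can be attenuated.

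The illustrative size is a cirrhosis odds ratio of 0.43–0.62 against a true 0.40. The lower end applies if RBV matters only in G1a and G4, the upper end if it also matters in G1b. This assumes an RBV odds ratio of 2 to 3 at least in G1a and G4 and an assumed regimen mix, which the documents do not give. Masking is possible but not established, and with an RBV effect confined to G1a and G4 it can be small. The primary SVR12 estimate is untouched. The change is worth making because it uses data already collected.

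**What to change.** In SAP 4.2.7.2.1:

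1. Delete the condition that ties regimen analyses to what remains in the final model, and the optional wording after it.
2. Always report, beside the planned model, a version with RBV (yes/no) kept in regardless of p-value. Add planned duration (12 or 24 weeks) where the 24-week group is large enough to estimate it, and set that minimum beforehand. Label both as adjustment terms, not treatment effects.
3. Add to Table 8 a table of SVR12 by regimen within genotype-by-cirrhosis cells, with counts and confidence intervals.
4. State that RBV cannot be separated from the factor in cirrhotic G1a and in G4, where the CP rules fix it.
5. Record the move from group-wise regressions to one pooled model as a change from the protocol.

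The cost is SAP wording, one more model and one more table. With about 21 to 42 non-responders the adjusted model will have wider intervals and in some settings less power. It is therefore reported alongside the planned model and does not replace it.
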